### **23 APPENDICES**

Appendix 1: Declaration of Helsinki

Appendix 2: Management of clinical trial during Pandemic COVID-19

Since December 2019, an outbreak of respiratory disease caused by a novel coronavirus, first detected in Wuhan City, Hubei Province, China, has been detected in nearly all countries of the world. The virus has been named "severe acute respiratory syndrome coronavirus 2 (SARS-CoV-2)" and the disease it causes has been named "Coronavirus Disease 2019" (COVID-19). On 08 March 2020, the World Health Organization declared the COVID-19 outbreak a global pandemic.

The COVID-19 public health emergency may impact the conduct of clinical trials of medical products. In response to the pandemic, various HA have issued guidelines to maintain the integrity of ongoing clinical studies.

MENARIN	Corporate Medical Department		
	]	Protocol Template	
Identification Number	Version Number	State	Effective date
FORM-000050125	2.0, CURRENT	Effective	08 Jan, 2021

### Study Code: MEIN/21/AmNe-Hyp/001

	7
	site during Visit 1 (screening).
	Each patient must be provided with new information that might impact their
	

willingness to participate in the study in a timely manner. Should the patient need to re-consent if permitted by investigative site procedures and local regulations, the informed consent form can be mailed to the patient.

The patient can sign the consent form at home and mail it to the study site.

	Alternatively, the PI or designee can visit the patient at home to present the changes to the study and obtain the informed consent form signature at the
	patient's home. If the patient has any questions about the changes to the study prior to providing their signature, they will be provided with an opportunity to discuss these questions with the PI or designee.
	After having obtained the consent, a copy of the signed consent must be sent to or stay with the patient.
Study Treatment Distribution and Return	This paragraph is not applicable for Visit 1 (screening) but only for the subsequent visits.
	Due to social restriction measures, the patient may not be able to reach the
	study site. In such cases, the study treatment will not be dispensed to the
	patients at the site. Instead, the study treatment may be distributed to the
	patients' home at the times defined in the Study flow chart by the designated
	site staff or by a distributor independent from, and acting on behalf of the
	Sponsor in line with national law or temporary national emergency measures.
	Patients will be informed and trained on the new dispensing procedures.
	Patients will be instructed to keep unused study treatment, which will be
	collected by the designated site staff on the earliest possible time or agreed
	with the patient to return to site via courier.
Study assessment and	The Screening visit is a mandatory in-clinic visit and therefore should be
procedures	performed at the site. The PI continues to be responsible for reviewing all
	study -related assessments.
	The patient may not be able to reach the site to perform blood pressure (BP)
	measurement for primary and secondary analysis, clinical laboratory tests,
	vital sign and physical examination, electrocardiogram (ECG), or other
	assessments required by the study flow chart. In such cases, these
	assessments will be performed by the health care professionals (study staff or
	qualified designee) at patient's home, if allowed per country regulations.
Remote Monitoring Visit	Study monitors may consider ongoing remote data review and remote data verification, where applicable and if site agreed with this approach, and if allowed per local regulations, to confirm that data entered into the eCRF by authorized study site personnel are accurate, complete, and wherever possible
	verifiable from source documents; that the safety and rights of participants

MENARINI	Corporate Medical Department		
	Protocol Template		
Identification Number	Version Number	State	Effective date
FORM-000050125	2.0, CURRENT	Effective	08 Jan, 2021

Study Code: MEIN/21/AmNe-Hyp/001

	are being protected; and that the study is being conducted in accordance with	
	the currently approved protocol and any other study agreements, ICH GCP,	
	and all applicable regulatory requirements. The procedures for remote data	
	review must be detailed in the monitoring plan.	
Data Quality Assurance	During the period of travel restrictions or social distancing, the Sponsor may	
	implement remote monitoring in place of on-site visits where available and if	
	allowed per local regulations, to assure the accuracy and completeness of the	
	data captured. Any such monitoring will be performed as per standard IQVIA	
	procedures and must documented in the monitoring plan.	
Abbreviations: $COVID-19 = C$	oronavirus Disease 2019; eCRF = electronic case report form; GCP = Good	
Clinical Practice; ICH = Internat	ional Council for Harmonisation; PI = Principal Investigator.

1. INTRODUCTION

This statistical analysis plan (SAP) describes the rules and conventions to be used in the presentation and analysis of efficacy and safety data for Protocol MEIN/21/AmNe-Hyp/001. It describes the data to be summarized and analyzed, including specifics of the statistical analyses to be performed.

This SAP is based on protocol version 1.0, dated 27 September 2021.

2. STUDY OBJECTIVES AND ESTIMANDS

2.1. Primary Objective

The primary objective is to assess the antihypertensive efficacy of the extemporaneous combination of nebivolol (NEB) 5 mg with amlodipine (AML) 5 mg or AML 10 mg in lowering the sitting DBP between Visit 2 (Week 0) and Visit 4 (Week 8) in patients with uncontrolled BP, previously treated with NEB 5 mg or AML 5 mg monotherapies for at least 4 weeks.

2.2. Secondary Objectives

The secondary objectives are

- To assess the antihypertensive efficacy of the extemporaneous combination of NEB 5 mg with AML 5 mg or AML 10 mg in lowering sitting SBP between Visit 2 (Week 0) and Visit 4 (Week 8) in patients with uncontrolled BP previously treated with NEB 5 mg or AML 5 mg monotherapies for at least 4 weeks.
- To assess the antihypertensive efficacy of the extemporaneous combination of NEB/AML 5/10 mg versus extemporaneous combination NEB/AML 5/5 mg, in lowering sitting DBP and SBP between Visit 3 (Week 4) and Visit 4 (Week 8) in patients with uncontrolled BP previously treated with NEB 5 mg or AML 5 mg monotherapies for at least 4 weeks.
- To assess the antihypertensive efficacy of the extemporaneous combination of NEB 5 mg with AML 5 mg or AML 10 mg by evaluating the patients who achieve BP goal (sitting BP < 130/80 mmHg) at Visit 2 (Week 0), at Visit 3 (Week 4), and at Visit 4 (Week 8).
- To assess the compliance to the treatment (percentage of actual doses taken versus doses to be

Document: \\weedc-vnasc01\Biosdata\Menarini\NebAml\ZZA67778\Biostatistics\Documentation\SAP\SAP_Menarini_MEIN21AmNe-Hyp001_Final_V1.0

Author: [name]

Version Number:

Final V1.0

Version Date:

11Nov2022

Template No.: CS_TP_BS016 Revision 7

Reference: CS_WI_BS005

Effective Date: 01Nov2021

taken) at Visit 2 (Week 0), at Visit 3 (Week 4), and at Visit 4 (Week 8).

- To evaluate the safety and tolerability of the monotherapies (NEB 5 mg and AML 5 mg) and of the extemporaneous combinations (NEB 5 mg and AML 5mg or AML 10 mg) after 8 weeks of treatment.

2.3.Exploratory Objectives

The exploratory objectives are

- To assess change in mean sitting DBP and SBP between Visit 1 (Week -4) and Visit 2 (Week 0), Visit 3 (Week 4) and Visit 4 (Week 8):
 1. In the group of patients who were on NEB 5 mg and AML 5 mg at Visit 1 and continued to be on the same therapies.
 2. In the group of patients who switched to NEB 5 mg or AML 5 mg from any other BBs or CCBs at Visit 1.
- To assess the change in mean sitting DBP and SBP between Visit 2 (Week 0) and Visit 3 (Week 4) for uncontrolled patients at Visit 3 (Week 4).
- To assess the antihypertensive efficacy of the extemporaneous combination of NEB 5 mg with AML 5 mg or AML 10 mg by evaluating the number of patients achieving the BP goal (sitting BP <130/80 mmHg) at Visit 2 (Week 0), Visit 3 (Week 4) and Visit 4 (Week 8):
 1. In the group of patients who were on NEB 5 mg and AML 5 mg at Visit 1 (Week -4) and continued to be on the same therapies.
 2. In the group of patients who switched to NEB 5 mg or AML 5 mg from any other BBs or CCBs at Visit 1 (Week -4).
- To assess the antihypertensive efficacy of the extemporaneous combination of NEB 5 mg with AML 5 mg or AML 10 mg by evaluating the number of patients divided into subgroups according to their hypertension grade, the presence of diabetes and/or of hypercholesterolemia achieving the BP goal (sitting BP <130/80 mmHg) at Visit 2 (Week 0), Visit 3 (Week 4), and Visit 4 (Week 8):
 1. In the group of patients who were on NEB 5 mg and AML 5 mg at Visit 1 and continued to be on the same therapies.
 2. In the group of patients, who switched to NEB 5 mg or AML 5 mg from any other BBs or CCBs at Visit 1.

Document: \\needc-vnasc01\Biosdata\Menarini\NebAml\ZZA67778\Biostatistics\Documentation\SAP\SAP_Menarini_MEIN21AmNe-Hyp001_Final_V1.0

Author: [name]

Version Number:

Final V1.0

Version Date:

11Nov2022

Template No.: CS_TP_BS016 Revision 7

Reference: CS_WI_BS005

Effective Date: 01Nov2021

3. STUDY DESIGN

3.1. General Description

This is a Phase IV, interventional, open-label, multicenter, multinational study with 2 study periods (a run-in period of 4 weeks and an assessment period of 8 weeks). Patients with hypertension with systolic blood pressure (SBP) ranging from ≥ 140 to ≤ 179 mmHg and diastolic blood pressure (DBP) ranging from ≥ 90 to ≤ 109 mmHg on treatment with any beta-blockers (BBs) or calcium channel blockers (CCBs) including NEB 5 mg or AML 5 mg for at least one month prior to Visit 1 will be screened for eligibility. On the same day of the Screening visit, eligible patients will enter into a run-in period after screening, during which:

- Patients receiving NEB 5 mg or AML 5 mg will continue the same therapy for 4 weeks.
- Patients on any other BBs or CCBs will be switched to NEB 5 mg or AML 5 mg.

Patients entering this phase in therapy with NEB 5 mg or AML 5 mg should be in a 1:1 ratio. After 4 weeks (± 2 days) of run-in period of monotherapy, BP will be further assessed at Visit 2. Patients with uncontrolled BP levels (sitting SBP/DBP $\geq 130/80$ mmHg) at Visit 2, with the treatment adherence (ranging between 80% to 120%) who did tolerate the treatment will enter into the assessment period and will be assigned to the extemporaneous combination of NEB 5 mg and AML 5 mg. Patients with controlled BP levels (sitting SBP/DBP $< 130/80$ mmHg) and/or who do not tolerate the treatment or have an adherence range below 80% or above 120%, will be withdrawn from the study. After 4 weeks ± 2 days in the assessment period, patients BP will be further evaluated at Visit 3: patients with controlled BP levels (sitting SBP/DBP $< 130/80$ mmHg) will continue the same extemporaneous combination, while patients with uncontrolled BP levels will be uptitrated from extemporaneous combination NEB/AML 5/5 mg to extemporaneous combination of NEB/AML 5/10 mg for further 4 weeks. At the end of the assessment period (8 weeks ± 4 days), Visit 4 will take place. To correctly evaluate the additional effect of the combination therapy, the number of patients with uncontrolled BP on NEB or AML monotherapy needs to be balanced at Visit 2. In order to maintain a 1:1 ratio during the assessment period, a cap of 110 patients for each treatment arm (ie. NEB and AML) will be included at Visit 2 in order to maintain a balanced number of uncontrolled patients entering the assessment period for each drug. The evaluation will be done every 50 patients. If the rate of entrance in the assessment period for one of the 2 tested drugs will deviate more than 5%, a corrective measure will be initiated: according to the enrolment site statistics, one or more sites will be informed to enroll a greater

Document:	\\weedc-vnasc01\Biosdata\Menarini\NebAml\ZZA67778\Biostatistics\Documentation\SAP\SAP_Menarini_MEIN21AmNe-Hyp001_Final_V1.0		
Author:	[name]	Version Number:	Final V1.0
		Version Date:	11Nov2022
Template No.:	CS_TP_BS016 Revision 7	Reference:	CS_WI_BS005
Effective Date:	01Nov2021		

number of patients being treated with the least represented drug in the assessment period. A total number of 290 patients will be screened considering 25% of drop-out rate, to obtain approximately 216 completed patients at the end of the study (Visit 4).

3.2. Schedule of Events

Schedule of events can be found in Section 2.2 of the protocol.

3.3. Changes to Analysis from Protocol

- The secondary and exploratory analysis use McNemar's test to analyze proportion of patients achieving BP goal (SBP/DBP <130/80 mmHg) between visit 2, visit 3, and visit 4. As per the entry criteria to the combination therapy, only those patients with uncontrolled BP (SBP/DBP \geq 130/80 mmHg) at visit 2 are eligible. So, the proportion of patients achieving the BP goal at visit 2 will be always zero. Thus, SAP has been updated with exact McNemar's test instead of McNemar's test when comparing the counts with respect to visit 2.
- As per protocol, the definition of Per Protocol Population is "All patients included in the Safety population who do not have any major protocol deviations that could affect the analyses.". In SAP, this has been updated to,
"The Per-Protocol (PP) population will contain all patients included in the Safety population who do not have any major protocol deviations that could affect the primary efficacy analyses and have at least baseline (Week 0) and Week 8 assessments with primary efficacy data".
- As per protocol, the definition of ENR Population is "Patients who are enrolled into the study (ie. signed ICF and met the eligibility criteria) and may or may not receive the study treatment (extemporaneous combination)." In SAP, this has been updated to,
"The Enrolled (ENR) population will contain all patients who are enrolled into the study (i.e. signed ICF and met the eligibility criteria) and may or may not receive the study medication (i.e., monotherapy and/or combination therapy). An enrolled patient who does not meet the inclusion/exclusion criteria might be included in the ENR population as per the investigator discretion."
- As per protocol, Compliance to study medication will be summarized for Enrolled and Safety populations. In SAP, this has been updated to consider the summary based on SAF and mITT because Safety population will include monotherapy patients and thus analysis on ENR is not required.

Document: \\ieedc-vnasc01\Biosdata\Menarini\NebAml\ZZA67778\Biostatistics\Documentation\SAP\SAP_Menarini_MEIN21AmNe-Hyp001_Final_V1.0

Author: [name]

Version Number:

Final V1.0

Version Date:

11Nov2022

Template No.: CS_TP_BS016 Revision 7

Reference: CS_WI_BS005

Effective Date: 01Nov2021

- As per protocol, exploratory efficacy analyses will be summarized for Enrolled population. In SAP, this has been updated to include summary based on mITT population as well.

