	To test the covariate effects and the effects of interactions between covariates on the primary efficacy endpoint (change in mean sitting DBP) as well as the first secondary efficacy endpoint (change in mean sitting SBP), a repeated measures general linear model (GLM) will be proposed. The GLM repeated measures procedure provides analysis of variance when the same measurement is made several times on each patient. Age, gender, body mass index, and baseline DBP will be included in the GLM model as covariates. The GLM model will be explained in detail in the Statistical Analysis Plan, approved before database lock.
	All the other continuous secondary/exploratory endpoints will be assessed across different study visits using a paired t-test or independent t-test, as applicable.
	All secondary/exploratory endpoints related to proportion of patients achieving the BP goal at Week 4 and Week 8 will be analyzed descriptively along with the relative 95% CI to assess if there is a significant difference from Week 0 where all patients were uncontrolled.
	Sample size : A total sample size of 216 patients is required to achieve 90% power at a 5% significance level assuming a difference in mean DBP from baseline (Visit 2) to 8 weeks (Visit 4) of 4 mmHg and a standard deviation for this difference of 10 mmHg. The mean change in DBP for the null hypothesis is set equal to 2 mmHg.

[figure not shown]
MENARINI	Corporate Medical Department		
	Р	Protocol Template	
Identification Number	Version Number	State	Effective date
FORM-000050125	2.0, CURRENT	Effective	08 Jan, 2021

A total number of 290 patients will be screened considering 25% of
drop-out rate, to obtain approximately 216 completed patients at the
end of the study (Visit 4).

MENARINI	Corporate Medical Department				
	Pr	otocol Template			
Identification Number	Version Number	State	Effective date		
FORM-000050125	2.0, CURRENT	Effective	08 Jan, 2021		

Study Code: MEIN/21/AmNe-Hyp/001

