and AML 5 mg. Patients with controlled BP levels (sitting SBP/DBP <130/80 mmHg) and/or who do not tolerate the treatment or have an adherence range below 80% or above 120%, will be withdrawn from the study.

After 4 weeks  $\pm 2$  days in the assessment period, patients BP will be further evaluated at Visit 3: patients with controlled BP levels (sitting SBP/DBP <130/80 mmHg) will continue the same extemporaneous combination, while patients with uncontrolled BP levels will be uptitrated from extemporaneous combination NEB/AML 5/5 mg to extemporaneous combination of NEB/AML 5/10 mg for further 4 weeks.

At the end of the assessment period (8 weeks  $\pm 4$  days), the patients will attend an End of Treatment Visit 4. To correctly evaluate the additional effect of the combination therapy, the number of patients with uncontrolled BP on NEB or AML monotherapy needs to be balanced at Visit 2. In order to maintain a 1:1 ratio during the assessment period, a cap of 110 patients for each treatment arm (ie. NEB and AML) will be included at Visit 2 in order to maintain a balanced number of uncontrolled patients entering the assessment period for each drug. The evaluation will be done every 50 patients. If the rate of entrance in the assessment period for one of the 2 tested drugs will deviate more than 5%, a corrective measure will be initiated: according to the enrolment site statistics, one or more sites will be informed to enroll a greater number of patients being treated with the least represented drug in the assessment period.

A total number of 290 patients will be screened considering 25% of drop-out rate, to obtain approximately 216 completed patients at the end of the study (Visit 4).

Sitting BP will be measured at all visits before blood sampling. BP will be measured in both arms at the Screening visit (Visit 1) in order to detect possible between-arm differences. The arm with the higher mean DBP will be used in all subsequent visits for BP assessment. Blood pressure measurements should be performed as nearly as possible within the same time frame of the day (7:00 to 12:00 a.m.), on the same arm, possibly by the same member of the site staff/personnel, and using the same calibrated equipment at each visit.

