6.5. Statistical Tests

The default significant level will be (5%); confidence intervals will be 95% and all tests will be two-sided, unless otherwise specified in the description of the analyses.

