16.2.2.3. Number and proportion of patients achieving the BP goal

The number of patients achieving the BP goal (sitting BP < 130/80 mmHg) will be summarized for Visit 2 (Week 0), Visit 3 (Week 4) and Visit 4 (Week 8) along with percentage and 95% CI (Clopper Pearson). A p-value using exact McNemar's test will be presented to compare the proportion of patients achieving the BP goal (sitting BP < 130/80 mmHg) between Visit 2 and Visit 3 as well as Visit 2 and Visit 4. A p-value using McNemar's test will be presented to compare the proportion of patients achieving the BP goal (sitting BP < 130/80 mmHg) between Visit 3 and Visit 4.

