16.3.2. Analysis of Exploratory Efficacy Variables

Exploratory efficacy variables will be summarized in a descriptive manner using ENR and mITT populations for Visits 1, 2, 3 and 4.

- Change in sitting DBP and SBP from Visit 1 (Week -4) will be using paired t-test. The p-value obtained from the paired t-test will be presented for the visits - Visit 2 (Week 0), Visit 3 (Week 4) and Visit 4 (Week 8). Assumption of Normality will be investigated using Wilk-Shapiro test. If the data is found to be non-Normal, then paired t-test will be replaced by Wilcoxon signed rank test. A descriptive summary using n, mean, median, SD, Q1, Q3, minimum, and maximum is also presented.
- Change in mean sitting DBP and SBP for uncontrolled patients between Visit 2 (Week 0) and Visit 3 (Week 4) will be using paired t-test. The p-value obtained from the paired t-test along with n, mean, median, SD, Q1, Q3, minimum, and maximum will be presented. Assumption of Normality will be investigated using Wilk-Shapiro test. If the data is found to be non-Normal, then paired t-test will be replaced by Wilcoxon signed rank test.
- The number of patients achieving BP goal (sitting BP < 130/80 mmHg) will be summarized for Visits 2, 3, and 4, along with percentage and 95% CI for the proportion. A p-value using exact McNemar's test will be presented to compare the proportion of patients achieving the BP goal (sitting BP < 130/80 mmHg) between Visit 2 and Visit 3 as well as Visit 2 and Visit 4. A p-value using McNemar's test will be presented to compare the proportion of patients achieving the BP goal (sitting BP < 130/80 mmHg) between Visit 3 and Visit 4.
- The number of patients achieving BP goal (sitting BP < 130/80 mmHg) will be summarized for Visits 2, 3 and 4, along with percentage for each of the subgroup specified under section 7.5 of the SAP.

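### McNemar p-values for BP-goal rates against Visit 2 carry no efficacy information, because the entry rule fixes the Visit 2 rate at zero; the switch to an exact test does not change that

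*SAP*

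**What the plan says.** Protocol section 5 removes controlled patients at Visit 2. It names this group as "Patients with controlled BP levels (sitting SBP/DBP <130/80 mmHg) and/or who do not tolerate the treatment", adds those with adherence outside 80% to 120%, and withdraws them all from the study.

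SAP 3.3 accepts what follows for anyone starting the combination: "So, the proportion of patients achieving the BP goal at visit 2 will be always zero". For that reason it adopts exact McNemar "when comparing the counts with respect to visit 2". SAP 16.2.2.3 then specifies: "A p-value using exact McNemar's test will be presented to compare the proportion of patients achieving the BP goal", for Visit 2 against Visit 3 and Visit 2 against Visit 4. Ordinary McNemar is kept for Visit 3 against Visit 4. Goal rates with Clopper-Pearson 95% intervals are shown at each visit. SAP 16.3.2 repeats the tests for the continued and switched groups: "Exploratory efficacy variables will be summarized in a descriptive manner using ENR and mITT populations". SAP 6.5 makes all tests two-sided at 5%.

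The tests originate in protocol 12.5.4 and 12.5.5, which ask for McNemar p-values between each pair of Visits 2, 3 and 4. The protocol synopsis describes the goal-rate analysis as descriptive with a 95% CI, but gives its aim as "to assess if there is a significant difference from Week 0 where all patients were uncontrolled". Neither document states a benchmark goal rate or makes any allowance for regression to the mean after selection on Visit 2 BP.

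**The concern.** McNemar's null hypothesis is that the goal rate is the same at the two visits. Here one of those rates is set to zero by the entry rule, so movement is possible in one direction only and a single later responder makes the null false. Rejecting it shows that some patients crossed 130/80. It does not show that the combination moved them. Patients were selected on a raised reading, so some may fall below the threshold later through visit-to-visit variation alone, and an unrandomized, open-label, single-sequence study has no control group to remove that.

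The exact test deals with a different problem: the chi-square approximation is poor when discordant counts are small. It leaves the null hypothesis as it was.

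What is at stake is interpretation. The protocol regards the proportion at target as an important marker of therapeutic success. A p-value beside it will be read as evidence of efficacy, even at a goal rate nobody would regard as a success. By my reading up to 12 such p-values are planned: 2 comparisons × 2 populations (mITT, PP) = 4 in SAP 16.2.2.3, and 2 comparisons × 2 populations (ENR, mITT) × 2 prior-therapy groups = 8 in SAP 16.3.2.

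**Working it through.** **Inputs from the documents**

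- Visit 2 goal rate among patients entering combination therapy: 0 (SAP 3.3). This holds whether uncontrolled means both components raised or either one, since neither kind of patient is below 130/80.
- Two-sided 5% tests (SAP 6.5); no imputation, so only observed visit pairs enter (SAP 7.3).
- N = 216 (protocol 12.2), used here only as a denominator. The documents do not size the goal-rate tests.

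**The plan's own figure.** For a DBP change of 4 against a null of 2 with SD 10, n = (10 × (1.645 + 1.282) / 2)² ≈ 214.1, so 215; the t-based figure is 216. The 216 therefore reproduces for a one-sided 5% test. Two-sided it would be 263 (265 t-based). That mismatch is a separate matter from this point.

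**Exact McNemar with an empty cell.** Let b be the patients at goal at Visit 2 but not later, and c those at goal later but not at Visit 2. By design b = 0 and c = k. Then p = 2 × P(Bin(k, 0.5) ≤ 0) = 2 × 0.5^k. The uncorrected test has chi-square (b − c)²/(b + c) = k on 1 df.

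| Responders k | k/216 | Exact p | Uncorrected McNemar p |
|---|---|---|---|
| 4 | 1.9% | 0.125 | 0.0455 |
| 5 | 2.3% | 0.0625 | 0.025 |
| 6 | 2.8% | 0.031 | 0.014 |
| 7 | 3.2% | 0.016 | 0.008 |
| 10 | 4.6% | 0.0020 | 0.0016 |

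The change of test moves the significance threshold from 4 responders to 6. With a continuity correction the older test also needed 6 (p = 0.041). N does not enter the formula. The Clopper-Pearson interval for 6/216 is 1.0% to 5.9%.

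**Chance of significance with an ineffective treatment.** If a share q falls below 130/80 with no drug effect, responders are Bin(216, q), and the test is significant when there are at least 6.

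| q | P(p<0.05) |
|---|---|
| 1% | 2% |
| 2% | 27% |
| 3% | 63% |
| 4% | 87% |
| 5% | 96% |
| 10% | >99.9% |

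**What q might be (assumption).** The documents give no BP means, no SBP variance and no correlations. The only SD stated is 10 mmHg for the DBP difference, which would mean 10/√2 = 7.07 per visit. I simulated no treatment effect with these assumed values: between-patient SD 10/7 (SBP/DBP), correlation 0.6, selection on uncontrolled BP below 180/110 at Visit 2, and two settings for the within-patient SD. Each range runs from uncontrolled read as both components raised to either raised.

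| Assumed mean before selection | Within-patient SD | q | P(p<0.05) |
|---|---|---|---|
| 140/87 | 10/7.07 | 6.9–9.7% | >99% |
| 145/90 | 10/7.07 | 4.1–5.5% | 87–98% |
| 150/92 | 10/7.07 | 2.3–3.1% | 38–66% |
| 155/95 | 10/7.07 | 1.1–1.5% | 4–10% |
| 140/87 | 5/3.5 | 2.1–4.6% | 31–93% |
| 145/90 | 5/3.5 | 1.0–2.1% | 2–30% |
| 150/92 | 5/3.5 | 0.5–0.9% | 0.1–1.6% |

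The false-significance rate thus runs from under 5% to over 99% within assumptions that cannot be ruled out from the documents.

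**ENR.** The zero is a property of patients starting the combination. SAP 5.1 does not require a combination dose for ENR, so ENR includes patients found controlled at Visit 2 and withdrawn. Its displayed Visit 2 rate can exceed zero and describes a different set of patients from the Visit 3 and Visit 4 rates.

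**The case against.** The other side has real points.

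- **The rate and interval are already planned.** The goal rate and its 95% CI will stand beside each p-value, and the documents call these analyses descriptive. No sample size or gatekeeping depends on them. That limits the harm, but a p-value that cannot bear on efficacy should still not be presented as a test at 5%.
- **Regression to the mean is not special to this test.** Selection on Visit 2 affects every comparison with Visit 2, including the primary. True. What is specific here is that the comparator is fixed at zero, so the null is false once any patient responds.
- **The size of the false-positive risk is unknown.** This stands. A reader might infer that chance crossing guarantees significance, or that a firm lower bound on the risk can be given. Neither follows: with higher BP or smaller within-patient variation the chance is a few percent or less.
- **Very few responders do not suffice.** A reader might infer that any responders at all produce significance. Five do not.
- **ENR.** A reader might infer that the ENR test itself mixes different patients. McNemar uses pairs, and withdrawn patients with no later visit form none. Protocol section 10 asks early discontinuers to complete the Visit 4 assessments, but SAP Appendix 1 lists Early Termination as its own visit. The problem is mainly in the displayed ENR rates.
- **Status of the endpoint.** Goal rate is one of several secondary endpoints. The documents do not label it key.

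**Conclusion.** The point holds, within limits. In patients entering combination therapy, the exact McNemar p-value against Visit 2 is 2 × 0.5^k. It falls below 0.05 at six responders, 2.8% of 216, whatever the cause of the responses. This is arithmetic from the SAP's own statement and needs no assumption about BP variability. The exact version improves the approximation only.

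How often an ineffective treatment would pass depends on inputs the documents do not give. Conditional on the chance-crossing rate, it is 27% at 2%, 63% at 3% and 96% at 5%.

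The Visit 3 versus Visit 4 comparison is not affected, since neither rate is fixed by entry. The subgroup tables carry no p-value in the SAP. A reader might infer that the goal rates themselves are uninformative or that the primary analysis fails on this account; the documents support neither. The rates with their intervals remain useful, and the point concerns secondary and exploratory analyses only. It should be corrected, but it does not threaten the trial's main result.

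**What to change.** 1. Delete the Visit 2 versus Visit 3 and Visit 2 versus Visit 4 McNemar p-values from SAP 16.2.2.3 and 16.3.2, with the matching code in Appendix 1.
2. Present the goal rates at Visits 3 and 4 with Clopper-Pearson 95% intervals as the result. They are already specified in 16.2.2.3; 16.3.2 should name the same method. Keep the Visit 3 versus Visit 4 comparison.
3. Record the deletion in SAP 3.3 as a departure from protocol 12.5.4 and 12.5.5, and drop the synopsis aim of showing a significant difference from Week 0 for goal rates.
4. In the ENR tables, state that the Visit 2 denominator includes patients withdrawn as controlled, and take the Visit 3 and Visit 4 rates from mITT.

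The cost is fewer p-values and one recorded departure from the protocol. No new data are needed. Protocol 12.7 requires a substantial amendment for changes to the primary endpoint or primary analyses, and this is neither.
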